#### Criteria for Potentially Clinically Significant Vital Sign Values Table C-2.

Vital Sign	Category	Criteria for Potential Clinically Significant Vital Signs
Systolic blood pressure	Low	Value $\leq$ 90 mmHg and/or decrease $\geq$ 20 mmHg from Baseline
	High	Value $\geq 160 \text{ mmHg}$ and/or increase $\geq 20 \text{ mmHg}$ from Baseline
Diastolic blood pressure	Low	Value $\leq$ 50 mmHg and/or decrease $\geq$ 10 mmHg from Baseline
	High	Value $\geq 100 \text{ mmHg}$ and/or increase $\geq 10 \text{ mmHg}$ from Baseline
Pulse	Low	Value $\leq$ 50 bpm and/or decrease $\geq$ 15 bpm from Baseline
	High	Value $\geq$ 120 bpm and/or increase $\geq$ 15 bpm from Baseline
Weight	High	>7% increase from baseline
	Low	> 7% decrease from baseline

#### Appendix D. Details for Historical Data Borrowing

Statistical methods for incorporating historical data in a new study include power prior [Ibrahim 2000], commensurate prior [Hobbs 2011] and robust mixture prior [Schmidli 2014]. All these methods are Bayesian approaches. We took a similar approach using meta-analytical-predictive method to summarize historical control data as a basis for informative prior for the control group and to determine the maximal number of subjects to be borrowed (effective sample size [Neuenschwander 2010]). For the treatment group, we use a noninformative prior so that information for the treatment group only depends on in-trial data [Baeten 2013]. We systematically evaluate the impact of bias (defined as the difference between historical control data and concurrent control data) and number of historical control subjects borrowed on the (Bayesian) type I error rate/false positive rate and power/true positive rate. So the number of subjects borrowed is determined to control the inflation (if any) of two types of error rates to a reasonable extent based on a reasonable range of the magnitude of bias.

## D-1 Historical Data Selection and Meta-Analysis

The historical data are carefully selected based on the similarity in target population, mechanism of action of study drugs, concomitant medications [Pocock 1976] between historical trials and the trial under design. The selection of historical trials is described in the following.

#### • ABBV-105 vs Placebo (Borrowing Placebo)

For placebo control group vs ABBV-105 treatment group, historical data for placebo group are available from three clinical trials at the time of design stage of the current trial. These historical control data consist of 349 subjects from three clinical trials with similar populations (TNF and/or Bio-IR on background MTX or csDMARDs), mechanism of action (JAK inhibition), and study designs: baricitinib Phase 3 study BEACON (n = 176, mean [SD] of DAS28-CRP change = -0.8 [1.5]) [Genovese 2016]; tofacitinib Phase 3 study STEP (n = 118, mean (SD) = -0.6 (1.5)) [Burmester 2013]; and upadacitinib-Phase II (n = 55, mean (SD) = -1.1 (1.6)) (AbbVie Study M13-550). The criteria for

relevant historical control data selection were evaluated and met for these trials and the trial under design. These studies have similar population (TNF and Bio-IR), similar inclusion and exclusion criteria and were conducted in the similar way as the current study as shown in Table D-1.

		Current Study			
Criteria	Baricitinib (BEACON P3)	Tofacitinib (STEP P3)	Upadacitinib (M13-550 P2)	ABBV-599 (M16-063 P2)	
Inc 1	Bio-IR	Bio-IR	Bio-IR	Bio-IR	
Inc 2	18 years or older	18 years or older	18 years or older	18 years or older	
Inc 3	Moderately to severely RAModerately to severely RAModerately to severely RA		Moderately to severely RA	Moderately to severely RA	
Inc 4	csDMARDs	Methotrexate	Methotrexate	csDMARDs	
Exc 1	haemoglobin < 100 g/L	haemoglobin < 90 g/L	haemoglobin < 90 g/L	haemoglobin < 90 g/L	
Exc 2	WBC < 2.5 × 10^9/L	WBC < 3.0 × 10^9/L	WBC < 3.0 × 10^9/L	WBC < 3.0 × 10^9/L	
Exc 3	platelet < 100 × 10^9/L	platelet < 100 × 10^9/L	platelet < 100 × 10^9/L	platelet < 100 × 10^9/L	
Exc 4	eGFR < 40 mL/min/ 1.73 m^2	eGFR < 40 mL/min/ 1.73 m^2	eGFR < 40 mL/min/ 1.73 m^2	eGFR < 40 mL/min/ 1.73 m^2	
Exc 5	AST/ALT > 1.5 × ULN	$AST/ALT > 1.5 \times ULN$	$AST/ALT > 1.5 \times ULN$	$AST/ALT > 2 \times ULN$	

 Table D-1.
 Major entry criteria for historical studies and Study M16-063

The meta-analysis shows that predicted estimated mean (SD) and 95% confidence interval for mean are -0.80 (1.5) and [-1.06, -0.54] (Figure D-1) based on Empirical Bayes estimator [Sidik 2007]. The estimated heterogeneity variance  $\tau^2 = 0.0297$  and historical effective sample size (the maximum number of subjects we could borrow) is 49 [Neuenschwander 2010].

#### Figure D-1. Meta-Analysis for Historical Placebo Data

• ABBV-599 vs upadacitinib (Borrowing upadacitinib)

For upadacitinib control group versus ABBV-599, historical data consist of 206 subjects on 15 mg from two upadacitinib studies (Phase 2: Study M13-550 Balance I and Phase 3: Study M13-542 Select Beyond). Upadacitinib-Phase II gives n = 52, mean (SD) = -2.2 (1.5), and upadacitinib-Phase III shows n = 154, mean (SD) = -2.37 (1.6). The meta-analysis results in the predicted mean (SD) and 95% confidence interval are -2.32 (1.57) and [-2.54, -2.11] (Figure D-2) based on Empirical Bayes estimator [Sidik 2007]. Since  $\tau^2 = 0$ , the historical effective sample size is 206.

#### Figure D-2. Meta-Analysis for Historical Upadacitinib Data

In addition, upadacitinib-Phase III study data becomes available after this study design. A sensitivity analysis will be performed to include placebo data from upadacitinib-Phase III study in the meta-analysis (n = 144, mean (SD) = -1.01 (1.3)).

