In the Phase 1 ABBV-105 multiple ascending dose study (Study M16-357), the Btk occupancy at steadystate was near 100% throughout the dosing interval at the 60 mg QD dose; in the ABBV-599 multiple ascending dose study (Study M16-044), the Btk occupancy of approximately 70% and 90% was maintained throughout the dosing interval at the 10 and 20 mg QD doses, respectively.

Following once-daily dosing of ABBV-105 5 mg, 20 mg, and 60 mg, peak Btk occupancy at steady-state is predicted to be 67%, 93%, and 99%, respectively, whereas steady-state trough Btk occupancy is predicted to be 58%, 83%, and 89%, respectively. Therefore, the ABBV-105 doses of 5, 20, and 60 mg were selected to satisfy the Btk-related exposure criteria, as well as to represent exposures that were found to be safe and well tolerated in the Phase 1 studies. The selected dose of the upadacitinib component of the ABBV-599 arm is 15 mg, based on the results of the upadacitinib RA Study M13-542.

In bDMARD-IR subjects with RA, upadacitinib 15 and 30 mg QD doses achieved superior responses to placebo in all primary and ranked secondary endpoints at Weeks 12 and 24. The upadacitinib 30 mg dose provided little additional incremental benefit over the 15 mg dose. Thus, for the ABBV-599 treatment arm, the 15 mg QD upadacitinib dose was selected to be co-administered with ABBV-105. A treatment arm of 15 mg QD upadacitinib with ABBV-105 placebo QD is included to provide an in-study reference to estimate the additive effect of the ABBV-599 combination relative to upadacitinib monotherapy.

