### • ABBV-599 vs upadacitinib (Borrowing upadacitinib)

For the upadacitinib control group versus ABBV-599, historical data consist of 206 subjects from two upadacitinib studies (Phase 2: Study M13-550 Balance I and Phase 3: Study M13-542 Select Beyond). Active upadacitinib treatment group of 15 mg is considered. The meta-analysis results in the predicted estimated mean (SD) and 95% confidence interval are -2.32 (1.57) and [-2.54, -2.11].

For this comparison, 40 historical placebo subjects will be borrowed, which targets control of false positive rate < 10% and not exceeding the study sample size 40. That is:  $n_h = 40$ ,  $\mu_h = -2.32$ , and  $\sigma_h = 1.57/\sqrt{40} = 0.25$ . Therefore the prior distribution for upadacitinib would be  $N(-2.32, 0.25^2)$ . For ABBV-599, a "flat" non-informative prior probability distribution will be assumed, resulting in the posterior distribution totally based on the data. A dynamic borrowing based on observed bias may be performed as supportive analysis.

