## 13.0 Version History

### Table 3.SAP Version History Summary

Version	Date	Summary		
1.0	29 May 2018	Original version		
2.0	16 Jul 2018	
 
The changes made between the second and the first version are:
 
Small editorial changes for readability and to maintain consistency with the protocol
 
Clarification of cutoff days for laboratory and vital sign values.
 
An update to the DMC evaluation checkpoints.
 
The addition of the OMERACT Criteria, which was referenced in the safety section, to the Appendix
 
		
3.0	13 June 2019	
 
The changes made between this and the previous version are:
 
An update to visits with ECG data collected in Section 9.6 to maintain consistency with the protocol
 
Addition of an interim efficacy analysis to maintain consistency with the protocol
 
Updated the AESI table to maintain consistency with the protocol
 
Updates to the historical borrowing methods detailed in Appendix D
 
Change of formatting to adhere to a new SAP template
 
		
4.0	23 Jan 2020	
 
The change made between this and the previous version are:
 
Updated Potential Clinically Important Criteria for safety endpoints in Appendix C
 
Removed interim analysis due to protocol amendment
 
Changed secondary endpoints from "Proportion of subjects achieving CR (DAS28 CRP) at Week 12" and "Proportion of subjects achieving LDA (DAS28 CRP) at Week 12" to "Proportion of subjects achieving CR (DAS28 CRP) at all visits" and "Proportion of subjects achieving LDA (DAS28 CRP) at all visits," respectively, as the summaries by visits are of interest.
 
Added "Proportion of subjects achieving LDA (DAS28 CRP) but not CR at all visits" as secondary endpoints, as these summaries are of interest.
 
Added AO analyses for DAS28 CRP and ACR20/50/70 response rates at all visits as sensitivity analyses per protocol.
 
Updated the criteria for Liver-Related Elevations to align with Immunology RA project conventions.
 
		

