In addition, a supportive analysis using dynamic borrowing will also be performed based on the observed r and extended Table D-3 (not presented). For example, if bias is positive and r = 0.6, we could borrow 50 historical sample size to control false positive rate within 10%. On the other hand, if bias is negative, we will not borrow (borrow 0). Overall, if borrowing provides a true positive rate above 34% and the false positive rate less than 10%, we conduct dynamic historical borrowing by picking up the appropriate borrowing sample size to achieve maximum true positive rate.

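### The supportive dynamic borrowing rule for ABBV-599 vs upadacitinib is asymmetric and conflicts with its own criterion; as a minor second point, the two arms of Study M13-542 are treated differently in the two priors

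*SAP*

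**What the plan says.** **Dynamic rule.** SAP 8.3.5.2 and Appendix D (D-2) use fixed borrowing of 40 historical upadacitinib subjects as the main borrowing analysis for ABBV-599 vs upadacitinib. The prior is N(-2.32, 0.25²), applied whichever way the bias runs. A dynamic version is supportive: optional in 8.3.5.2, planned in Appendix D. D-2 says that at r = 0.6 positive, 50 subjects could be borrowed, and then that "if bias is negative, we will not borrow (borrow 0". It closes with a general criterion: where borrowing gives a true positive rate above 34% and a false positive rate below 10%, choose the size that maximises the true positive rate. The choice rests on an extended Table D-3 that the SAP does not present.

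**Study M13-542.** The upadacitinib prior draws on two trials: "Phase 2: Study M13-550 Balance I and Phase 3: Study M13-542 Select Beyond". The second supplies 154 of the 206 subjects. The primary placebo prior, N(-0.80, 0.335²), rests on three other placebo arms. Of the M13-542 placebo arm (n = 144, mean -1.01, SD 1.3), the SAP says that the data arrived after the design and that "A sensitivity analysis will be performed to include placebo data from upadacitinib-Phase III study in the meta-analysis". Protocol 4.2 chooses the upadacitinib dose "based on the results of the upadacitinib RA Study M13-542". The SAP version history lists, for version 3.0 of 13 June 2019, "Updates to the historical borrowing methods detailed in Appendix D".

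**The concern.** In Table D-3 the plus direction raises both the false positive and the true positive rate. Plus therefore means that history shows less improvement than the concurrent upadacitinib arm, so borrowing enlarges the ABBV-599 effect. Minus means the reverse. A rule that borrows on plus and not on minus uses history only when it helps the test arm, so it is biased even when history and trial agree. Such an analysis cannot corroborate the fixed-borrowing result. The conflict with the general criterion also means that two analysts could borrow 0 or 50 from the same data.

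For M13-542, both arms come from one trial, so the date on which its data arrived cannot by itself justify using one arm in a primary prior and not the other. The placebo prior matters because the borrowed placebo posterior is the primary input to MCP-Mod (SAP 8.3.5.3).

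**Working it through.** **Inputs (SAP Appendix D).** ABBV-599 to upadacitinib 60:40, so k = 1.5; α = 0.05; 1-β = 39%; δ = 0.33; historical mean -2.32, SD 1.57. With n_h borrowed, a0 = n_h/(n_h + 40).

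**Reproducing Table D-3.** Formulas (1) and (2) at r = 0.6 with 40 borrowed give false positive rates of 0.009 (minus) and 0.087 (plus), and true positive rates of 0.241 and 0.612, as printed.

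**The conflict.** Take r = 0.1 negative with 40 borrowed, so a0 = 0.5. The sum of quantiles is 1.645 - 0.279 = 1.366, the root term √(1 + 1.5 × 0.5) = 1.323, and the denominator √(1 + 1.5 × 0.25) = 1.173.
- (1): (-√2 × 0.1 × 0.5 × 1.366 - 1.645 × 1.323)/1.173 = (-0.097 - 2.176)/1.173 = -1.94, so the false positive rate is 0.026.
- (2): (√2 × 0.95 × 1.366 - 2.176)/1.173 = (1.835 - 2.176)/1.173 = -0.29, so the true positive rate is 0.385.

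Both limits are met. At r = 0.2 negative the rates are 0.022 and 0.354, which also qualify. With sizes capped at 50, the criterion borrows up to r of about 0.25 negative.

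**Size of the bias with no true bias.** The standard error of the observed r is (1.57/√40)/0.33 = 0.248/0.33 = 0.75, so the sign of r is largely noise. As a rough guide, borrowing 40 only when r is positive would shift the control mean by 0.5 × 0.399 × 0.248 = 0.05. The actual rule borrows less as r grows, so the shift is smaller. Simulation of the trial means (SD 1.57, success at posterior probability above 0.95) gives:

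| Rule | Shift in difference | False positives |
|---|---|---|
| Fixed borrowing of 40 | 0.00 | about 3.2% |
| Literal rule, sizes up to 50 | about -0.034 | 5.2-5.3% |
| Literal rule, sizes up to 200 | about -0.038 | about 5.6% |
| General criterion alone | about -0.031 | 5.4-6.0% |
| Same size for +r and -r, both limits met in both directions | 0.00 (within 0.001) | about 5-6% |

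The fixed figure can be checked by hand: -1.645 × √[(1/60 + 1/80)/(1/60 + 0.5/80)] = -1.856, or 3.2%. As a share of δ, 0.034/0.33 = 10% and 0.038/0.33 = 12%. Choosing sizes in steps of one up to 206 raises the literal shift to -0.044.

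The criterion alone stays biased because on the plus side more borrowing always raises the true positive rate, and only the 10% limit stops it. On the minus side the 34% floor stops borrowing early. With sizes up to 50, the mean number borrowed is about 38 for positive r and 13 for negative r.

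**Placebo prior.** The inputs are "baricitinib Phase 3 study BEACON (n = 176, mean [SD] of DAS28-CRP change = -0.8 [1.5"; "tofacitinib Phase 3 study STEP (n = 118, mean (SD) = -0.6 (1.5"; "upadacitinib-Phase II (n = 55, mean (SD) = -1.1 (1.6)) (AbbVie Study M13-550". Empirical Bayes random-effects pooling gives -0.797, 95% CI -1.056 to -0.538, τ² 0.0297 and effective sample size 48.6, matching the SAP (-0.80, -1.06 to -0.54, 0.0297, 49). Adding M13-542 gives -0.86, CI -1.07 to -0.65, τ² 0.0257 and effective sample size about 56. With 20 borrowed and 20 concurrent placebo subjects, the effect moves by 0.5 × 0.06 = 0.03.

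If the true placebo mean were -1.01, the false positive rate would be Φ[(0.5 × 0.21 - 1.645 × 0.335)/0.290] = 6.2% with the -0.80 prior, and about 5.0% with -0.86.

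**The case against.** A reader might infer that historical data are used in one direction throughout, always in favour of the sponsor's drugs. The documents do not support that.
- Fixed borrowing ignores direction.
- Including the M13-542 upadacitinib arm moves the comparator prior from -2.20 (M13-550 alone) to -2.32. That costs ABBV-599 about 0.5 × 0.12 = 0.06, twice what the placebo omission gives ABBV-105.
- Under the dynamic placebo rule and Table D-2, r = 0.4 leads to 50 borrowed if negative and 20 if positive.
- The placebo omission is disclosed with its figures and a committed sensitivity analysis, and keeping a design-stage prior is defensible. The gap of 0.21 lies within the 0.26 bias limit that the SAP evaluated.
- The version history does not show that the placebo prior was reopened in 2019.

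The no-borrowing sentence can also be read as the other half of the r = 0.6 example. There it agrees with the general criterion: at r = 0.6 to 0.7 negative, no borrowed size in Table D-3 reaches 0.34. That reading is fair, but the sentence names no value of r, whereas the matching placebo example names r = 0.5 in each direction. Nor does the reading remove the problem, since the criterion alone leaves most of the shift.

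The consequences are limited. The analysis is supportive, the comparison is an additional one outside the two ranked primary tests, and false positives at zero true bias stay well below the SAP's 10% target.

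**Conclusion.** The dynamic upadacitinib rule is asymmetric on either reading, and its two statements conflict at small negative r. With no true bias it overstates the ABBV-599 advantage by about 0.03 to 0.04 DAS28 units and loses the low false positive rate of fixed borrowing. The size is modest, but the analysis cannot serve as independent support for the fixed-borrowing result. These figures assume a common SD of 1.57 and a grid of sizes, because the extended table is not shown.

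The M13-542 inconsistency is real but minor: 0.06 in the placebo prior and 0.03 in the ABBV-105 effect. It assumes that the upadacitinib Phase III study with the placebo arm is M13-542, as the SAP's labels indicate. Table D-1 has no column for that trial, so there may be a reason to keep it apart, but the SAP does not state one. The first primary test, ABBV-599 vs placebo by MMRM, is untouched by either point.

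**What to change.** In Appendix D, replace both the no-borrowing sentence and the general criterion with one rule that depends on |r| only. For example: borrow the largest size on a stated grid for which formula (1) is below 10% and formula (2) above 34% in both directions at the observed |r|; otherwise borrow 0. State the grid and cap, and present the extended table. Deleting the no-borrowing sentence alone is not enough.

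The cost is less borrowing when the observed bias is positive. With a cap of 50, the mean on that side falls from about 38 to about 13, the same as on the negative side. False positives stay at about 5-6%. The symmetric rule removes the shift when history and trial agree; it does not guarantee zero bias when they differ.

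For M13-542, either treat both arms alike in the primary priors or state why they differ. If the placebo arm is added, the cost is one rerun meta-analysis and about 2.5 points of borrowed pairwise power (84.7% to 82.2% at an effect of 0.85 if true placebo is -0.80). Both changes are SAP wording and should be made before unblinding, so that the choice cannot be called data-driven.

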#### D-2 Borrowing size and prior distribution determination

For the primary analysis, our principle for fixed borrowing historical sample size is not to exceed the sample size in the current study. For placebo control borrowing, the fixed historical placebo borrowing sample size will not exceed 20. The upadacitinib fixed historical borrowing will not exceed 40.

• ABBV-105 vs Placebo (Borrowing Placebo)

Assume the mean for ABBV-105 is -1.65 and for placebo is -0.80 (from meta-analysis) so the absolute effect size is  $\delta = 0.85$ . Let *r* define the relative bias from historical data, i.e.,  $|\mu_C - \mu_h| = r\delta$  where  $\mu_C$  is the true but unknown mean for control group (placebo) and  $\mu_h$  is the historical data mean calculated from meta-analysis. To assess the bias impact on historical data borrowing, a reasonable limit for bias  $r\delta$  would be the half confidence interval width from meta-analysis i.e.,  $r\delta \leq 0.26$ . So

$$r \le 0.26/0.85 = 0.31.$$

Let  $a_0 = \frac{n_h}{n_h + n_c}$  be the proportion of borrowed number of historical patients  $(n_h)$  among all control patients  $(n_h + n_c$  where  $n_c$  is the number of control group subjects in current study). Let  $\mu_T$  and  $n_T$  be the treatment group mean and the number of subjects. Given r, and  $a_0$ , we can obtain Bayesian type I error rate/false positive rate (i.e., the probability achieving  $P(\mu_T - \mu_c < 0|Data) > 1 - \alpha$  under the null hypothesis  $\mu_T = \mu_c$ ):

$$\Phi\left[\frac{\pm\sqrt{2}ra_0\left(\Phi^{-1}(1-\alpha)+\Phi^{-1}(1-\beta)\right)-\Phi^{-1}(1-\alpha)\sqrt{1+k(1-a_0)}}{\sqrt{1+k(1-a_0)^2}}\right] \tag{1}$$

and Bayesian power/true positive rate (i.e., the probability achieving  $P(\mu_T - \mu_C < 0 | Data) > 1 - \alpha$  under the null hypothesis  $\mu_C - \mu_T = \delta$ ):

$$\Phi\left[\frac{\sqrt{2}(1\pm ra_0)\left(\Phi^{-1}(1-\alpha)+\Phi^{-1}(1-\beta)\right)-\Phi^{-1}(1-\alpha)\sqrt{1+k(1-a_0)}}{\sqrt{1+k(1-a_0)^2}}\right].$$
 (2)\*

The  $\pm$  in above formula corresponds to two directions of the bias,  $\alpha$  and  $1 - \beta$  are type I error and power for sample size calculation without borrowing, and  $k = n_T/n_C$  is the randomization ratio in current study with reduced control group due to borrowing.

\* (1) and (2) could be derived as follows:

Probability of trial success =  $P(P(\mu_T - \mu_C < 0 | Data) > 1 - \alpha)$ 

$$= \Phi\left(\frac{\mu_{c} - \mu_{T}}{\sigma\sqrt{\frac{1}{n_{T}} + \frac{1 - a_{0}}{n_{h} + n_{c}}}} - \frac{a_{0}(\mu_{h} - \mu_{c})}{\sigma\sqrt{\frac{1}{n_{T}} + \frac{1 - a_{0}}{n_{h} + n_{c}}}} - \Phi^{-1}(1 - \alpha)\frac{\sqrt{\frac{1}{n_{T}} + \frac{1}{n_{h} + n_{c}}}}{\sqrt{\frac{1}{n_{T}} + \frac{1 - a_{0}}{n_{h} + n_{c}}}}\right)$$

The treatment group sample size  $n_T = \frac{2(\Phi^{-1}(1-\alpha)+\Phi^{-1}(1-\beta))^2 \sigma^2}{\delta^2}$  which is the balanced sample size without borrowing. With  $k = n_T/n_c$ , the power without borrowing equals

$$\Phi\left[\sqrt{\frac{2}{1+k}}\left(\Phi^{-1}(1-\alpha)+\Phi^{-1}(1-\beta)\right)-\Phi^{-1}(1-\alpha)\right].$$

With  $k = n_T/n_C$ ,  $|\mu_C - \mu_h| = r\delta$  and  $a_0 = \frac{n_h}{n_h + n_c}$ , (1) could be derived for  $\mu_T - \mu_C = 0$  and (2) could be obtained from  $\mu_C - \mu_T = \delta$ .

		r =	0.1			r = 0.2			r = 0.3			
Borrowing # of	Err	or I	Por	wer	Err	or I	Po	wer	Err	or I	Po	wer
Subjects	_	+	_	+	_	+	_	+	_	+	_	+
0	0.05	0.05	0.65	0.65	0.05	0.05	0.65	0.65	0.05	0.05	0.65	0.65
10	0.028	0.041	0.741	0.793	0.023	0.049	0.712	0.816	0.019	0.058	0.682	0.838
20	0.021	0.040	0.796	0.868	0.014	0.053	0.753	0.896	0.010	0.071	0.706	0.920
30	0.018	0.041	0.831	0.907	0.011	0.060	0.780	0.934	0.007	0.085	0.722	0.955
40	0.016	0.044	0.853	0.929	0.010	0.067	0.798	0.954	0.005	0.099	0.734	0.971
50	0.016	0.047	0.868	0.943	0.009	0.074	0.811	0.965	0.005	0.113	0.742	0.980
		r =	0.4		r = 0.5			r = 0.6				
Borrowing # of	Err	or I	Po	wer	Err	or I	Po	wer	Err	or I	Po	wer
Subjects	_	+	_	+	_	+	_	+	-	+	-	+
0	0.05	0.05	0.65	0.65	0.05	0.05	0.65	0.65	0.05	0.05	0.65	0.65
10	0.015	0.069	0.651	0.858	0.012	0.080	0.619	0.876	0.010	0.094	0.587	0.893
20	0.007	0.093	0.655	0.939	0.004	0.119	0.600	0.954	0.003	0.150	0.544	0.967
30	0.004	0.118	0.657	0.970	0.002	0.158	0.588	0.980	0.001	0.206	0.515	0.988
40	0.003	0.142	0.660	0.982	0.001	0.195	0.579	0.990	0.001	0.258	0.495	0.994
50	0.002	0.163	0.662	0.989	0.001	0.227	0.573	0.994	0.000	0.303	0.481	0.997

